6.1 Sample Size

As a pilot study, the planned sample size is not based on statistical power to detect specified effect sizes on intervention outcomes. Rather, the planned sample of 80 subjects per intervention group was selected in terms of pilot study feasibility. The planned sample is considered more than sufficiently adequate to address pilot trial questions related to feasibility (of study recruitment and conduct, delivery of intervention, data collection) and estimates of trial-related parameters, along with 95% confidence intervals (mean intervention effect size, variance in outcome measures in the study population, within-facility correlation in outcome measures, within-patient correlation in outcome measures). As pilot studies are well known to over-estimate intervention effect sizes and under-estimate measures of variance, it is crucial that confidence intervals (precision of the estimates) are also calculated and available for planning of larger studies.

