3.0 STUDY DESIGN

The research will be conducted as a 12-week field study in eight Silverado dementia care facilities in Los Angeles and Orange County. Silverado is an assisted living service provider that delivers care for those with Alzheimer, dementia and other memory-impairing diseases. Data collection will occur twice during the study: baseline measures at the beginning of the study and outcome measures at the end of the study.

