4.0 TREATMENT OF SUBJECTS

4.1 Intervention Group

At two facilities, the active light intervention will enlist staff to increase daylight exposure to Alzheimer residents by taking them to daylit perimeter room in the morning (8:00 - 10:00 AM) where vertical daylight illuminance at eye level exceeds 2500 lux and where direct sun exposure

can be avoided. The intervention will consist of two hours of daylight exposure administered beginning at 8:00 AM in the morning each day (7 days / week) over the 12-week study.

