5.0 SELECTION AND EXCLUSION OF SUBJECTS

5.1 Inclusion criteria for enrollment

The trial inclusion criteria is an AD diagnosis and no physical co-morbidities that preclude participation in the daily group intervention. Based on current facility records, we estimate the intervention and control groups will include approximately 160 Alzheimer disease participants total (20 patients per facility). Demographic information obtained during the study preparation phase (mean age, gender, type of dementia by diagnosis, depression level, length of time in facility, date of onset of dementia, ethnicity) will be obtained to show that the facilities are comparable.

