6.0 STATISTICS

All analyses will include factors for facility and intervention (nested within facility). Baseline analyses will include descriptors of the study sample (age, gender, ethnicity, onset of Alzheimer's disease) as well as initial levels of the outcome measures (depression, cognition, behavior) and will utilize analysis of variance for continuous data and chi-square methods for categorical data to compare the intervention groups. If the intervention groups are found to differ on baseline levels of the outcome variables or other variables related to outcome, these variables will be included as adjusting covariates in the comparisons of 12-week outcomes. 12-week outcomes will be compared between intervention groups with analysis of variance (2-level factor for intervention, 8-level factor for facility, with intervention nested within facility). For planning of larger trials, the following estimates will be made (along with 95% confidence intervals) for each patient outcome: intervention effect size (mean group difference in outcome), variance in outcome (across patients, across facilities), within-facility correlation in outcomes (correlations in outcomes amongst patients within a facility), within-patient correlation in outcomes (repeated measures, baseline and 12-weeks).

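### Section 6.1 calls the sample ample for estimating within-facility correlation and effect size, but these and across-facility variance rest on eight facilities (6 degrees of freedom)

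*Combined protocol and SAP*

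**What the plan says.** Section 3.0 describes a "12-week field study in eight Silverado dementia care facilities". Section 5.1 expects "approximately 160 Alzheimer disease participants total (20 patients per facility"). Under Sections 4.1 and 4.2 a facility delivers either the daylight sessions or the control sessions to its residents, so the condition is assigned by facility.

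Section 6.1 says that "the planned sample of 80 subjects per intervention group was selected in terms of pilot study feasibility" and that "the planned sample size is not based on statistical power to detect specified effect sizes on intervention outcomes". It then says: "The planned sample is considered more than sufficiently adequate to address pilot trial questions". That sentence goes on to cover feasibility and also trial parameters with 95% confidence intervals: the mean intervention effect, outcome variance, within-facility correlation and within-patient correlation. Section 6.0 plans the same estimates, including "within-facility correlation in outcomes (correlations in outcomes amongst patients within a facility"), and adds outcome variance across facilities. Its model for the 12-week outcomes has a "2-level factor for intervention, 8-level factor for facility, with intervention nested within facility".

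Neither section gives an assumed ICC or an expected interval width, and neither names the number of facilities as the limit on precision.

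**The concern.** The only sample figure in Section 6.1 is a count of residents. Three of the quantities that Sections 6.0 and 6.1 plan to estimate are governed mainly by the count of facilities: the within-facility correlation, the across-facility variance and the difference between arms. Adding residents to the same eight facilities does little for them.

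This matters because Section 4.3 lists estimates and confidence intervals for trial planning among the study's outcomes, and Section 6.0 says they are meant for larger trials. A planner who accepts the adequacy statement could carry forward an ICC that the pilot can hardly distinguish from zero or from a very large value.

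**Working it through.** **The plan's own figure.** 8 facilities × 20 residents = 160, and 160 / 2 = 80 per group, as Section 6.1 states. The head count is consistent. The plan gives no precision figure to reproduce.

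**Inputs.**
- Facilities: 8 (Sections 3.0 and 6.0).
- Residents per facility: m = 20 (Section 5.1).
- Facilities per arm: 80 / 20 = 4 (derived).
- Confidence level: 95% (Section 6.0), taken as two-sided.
- ICC: not in the documents. Assumed at 0, 0.01, 0.05 and 0.10.
- Facilities are taken to be of equal size, with no attrition.

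**Degrees of freedom.** Between facilities within arms: 8 − 2 = 6. Within facilities: 8 × 19 = 152. The figure of 6 needs no assumption about the ICC.

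**ICC.** This is the exact F-based interval for a one-way layout, adjusted for arm. An observed ICC corresponds to F = 1 + 20 × ICC / (1 − ICC). The 2.5% and 97.5% points of F on 6 and 152 df are 0.204 and 2.492. The limits are (F_L − 1)/(F_L + 19) and (F_U − 1)/(F_U + 19), with F_L = F / 2.492 and F_U = F / 0.204. Negative lower limits are set to 0.

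Example at ICC 0.05: F = 1 + 20 × 0.05 / 0.95 = 2.053, F_L = 0.824, F_U = 10.04. The lower limit is −0.176 / 19.824 = −0.009, set to 0. The upper limit is 9.04 / 29.04 = 0.31.

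| Observed ICC | F | 95% interval for ICC |
|---|---|---|
| 0.01 | 1.202 | 0 to 0.20 |
| 0.05 | 2.053 | 0 to 0.31 |
| 0.10 | 3.222 | 0.01 to 0.42 |

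At an observed ICC of 0.05, the design effect 1 + 19 × ICC for a later trial with 20 per facility would run from 1.0 to 1 + 19 × 0.311 = 6.9. By simulation, about 70% of such pilots would have a lower limit of 0 if the true ICC were 0.05, and about 89% if it were 0.02.

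**Across-facility variation.** The 95% interval for the between-facility mean square runs from 6 / 14.45 = 0.42 to 6 / 1.237 = 4.85 times its estimate, using the chi-square points on 6 df. This holds for any ICC.

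**Effect size.** In units of the outcome SD, without covariates, the half-width is t(0.975, 6 df) × √(2 × [1 + 19 × ICC] / 80), with t = 2.447.

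| ICC | 1 + 19 × ICC | Standard error (SD) | Half-width (SD) |
|---|---|---|---|
| 0 | 1.00 | 0.158 | 0.39 |
| 0.01 | 1.19 | 0.172 | 0.42 |
| 0.05 | 1.95 | 0.221 | 0.54 |
| 0.10 | 2.90 | 0.269 | 0.66 |

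**Sensitivity to attrition.** With 16 residents per facility and ICC 0.05, the ICC interval is 0 to 0.33 and the effect half-width is 0.57 SD. The change is small because the facility count dominates.

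**Where the point does not apply.** Patient variance within facilities has 152 df, with an interval of about 0.81 to 1.27 times its estimate. A within-patient correlation of 0.5 would have an interval of roughly 0.37 to 0.61, ignoring clustering.

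**The case against.** The strongest reply is that this is a declared pilot with no power target, that its head count is arithmetically right, and that the plan already guards against misuse. Section 6.1 itself warns that pilots tend to overstate effects and understate variance, and treats reporting of intervals as essential. Section 6.0 commits to 95% intervals for the effect, across-facility variance and within-facility correlation. A correctly computed ICC interval of 0 to 0.31 would itself tell a later planner that the ICC is poorly known.

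Much of this stands. The absence of a power calculation is not a defect here, and the planned intervals reduce the harm. They do not make the advance statement of adequacy true.

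A reader might also infer three stronger things that the documents do not support:
- That the effect-size interval would be nearly uninformative. That description fits the ICC and across-facility variance. For the effect, total width is about 0.8 to 1.3 SD over ICC 0 to 0.10, which is wide but not empty.
- That the plan treats the 160 residents as independent. Section 6.0 puts facility in every analysis, and Section 6.1 derives no precision from 80 per group.
- That precision should be judged on four facilities, because Section 4.1 reads "At two facilities, the active light intervention will enlist staff to increase daylight exposure to Alzheimer residents" and Section 4.2 speaks of two others. This contradicts the eight in Sections 3.0 and 6.0 and must be reconciled, but it is a separate point. The present one holds with all eight.

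**Conclusion.** The point holds for three parameters: the within-facility correlation, the across-facility variance and the intervention effect. The first two would be barely estimated, while the effect would be estimated with a wide interval. The 6 degrees of freedom and the 0.42 to 4.85 range for the between-facility mean square follow from eight facilities in two arms. The ICC and effect-size intervals also rest on 20 residents in each facility and on assumed ICCs, and the effect widths on four facilities per arm and no covariate adjustment. The adequacy statement is a qualitative judgement that goes too far, not an arithmetical error. Nothing here questions its use for within-patient correlation. Feasibility rates such as recruitment and attrition were not checked, so no conclusion is drawn about them. Trial conduct is unaffected, but the statement should be corrected because planning estimates are among the study's stated outcomes.

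**What to change.** Restate Section 6.1 so that:
- the adequacy statement no longer covers within-facility correlation, across-facility variance or intervention effect size;
- it says that these three rest on the number of facilities, with 6 degrees of freedom if eight take part;
- it gives the expected 95% interval widths over an ICC range of 0.01 to 0.10, with the ICC labelled as an assumption;
- it says that the effect-size interval will be based on variation between facilities, and Section 6.0 is worded to match.

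The cost is wording only. The stated precision becomes less favourable, and no extra patients are needed. The facility count in Sections 4.1 and 4.2 should be reconciled with Sections 3.0 and 6.0 first, because the degrees of freedom and widths depend on it.

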7.0 ASSESSMENT OF SAFETY

The proposed study does not include any drug or device treatment and presents minimal (if any) risk to participants.

8.0 DISCONTINUATION OF THE STUDY

Participants do not have to remain in the intervention spaces if they do not want to while participating in the study. The informed consent form indicates to the Legally Authorized Representative (LAR) that he/she may withdraw his/her consent at any time and discontinue the participation of his/her family member without penalty.

9.0 ETHICS

All study staff are trained and credentialed to perform the duties assigned to them. In our proposed study, we are obtaining informed consent and HIPAA authorization from the legal representative of the participants in the study. All study staff have fulfilled the training mandated by their respective departments or institutions. Participant privacy and data confidentiality will be addressed via the following methods:

- Research procedures will be conducted in person in a private setting.
- Data will be captured and reviewed in a private setting.
- Only authorized research study personnel will be present during research related activities.
- The collection of information about participants is limited to the amount necessary to achieve aims of the research.
- Participants will not be approached in a setting or location that may constitute an invasion of privacy or could potentially stigmatize them.

10. DATA HANDLING AND RECORD KEEPING

All data will be coded and the key codes kept separately and securely. Research data will be protected against inappropriate use or disclosure via the following methods:

- Locked office
- Restricted access to authorized study personnel
- Secure computer/laptop
- Individual ID plus password protection
- Security software (firewall, antivirus, anti-intrusion) is installed and regularly
- updated in all servers, workstations, laptops, and other devices used in the study
- Restrictions on copying study related materials

